Data will be collected automatically from primary clinical systems within each Trust. NHS staff will enter data into clinical systems during routine clinical care of patients, or data will be generated as a result of clinical tests. Data in the primary clinical systems will be processed in accordance with each Trusts clinical guidelines and subject to local quality and governance procedures. Data will be extracted automatically and validated processes for data extraction, transformation and loading (ETL) have been designed to import the data into the local secure data stores.

Access to Local data stores

Access to identified data will be limited to those justified and approved by the local information governance teams and will always be NHS staff in accordance with the duty of confidentiality required by law. Anonymisation procedures will be automated after implementation.

Local data stores will be the only areas that hold any patient identifiers. De-identification is completed at this stage prior to passing data into any research databases and datasets.

De-identification

The data will be pseudonymised locally within each Trust; anonymisation processes will be automated and set up by NHS staff in accordance with:

- advice from local information governance procedures
- the HIC Standard Operating Procedure (SOP) for data sharing and anonymisation
- the Clinical data transfer policy

The data items summarised in Table 1 will be anonymised. Anonymisation will be approved locally by information governance teams before data are sent externally to ICHNT. De-identified data are then shared in accordance with the overarching data sharing agreement.

Each site will hold two versions of the database, one identifiable and one with de-identified, pseudonymised data. The de-identified version is for use in research and shared with the central research database at ICHNT. The identifiable database is held so that if necessary patients can be re-identified if it is of importance to re-contact the patient via their care team (please refer to 're-contacting patients' section).

NHS numbers and hospital numbers are pseudonymised using locally approved procedures. Names are removed from the dataset and date of birth is transformed to year of birth. Date of death is shared, however is converted in to relevant survival rates on provision of data to researchers. Researchers will never see the full date of

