Data access for research

TROP-RISK STUDY dataset

All analyses for the TROP-RISK STRUDY will be completed on fully de-identified data. This includes further de-identification to remove dates.

A designated clinical researcher ([name]) will freeze a copy of the database on 1st April 2017, so a static dataset can be used for analysis. This will be retained separately from the live database to allow reproducible analyses.

The study dataset will comprise all patients who had a troponin measured at each of the five academic centres between 2010 (2008 for University College Hospital) and 2017.

Dates will be converted to delta dates, with date zero being the date of the first troponin test. All further dates are provided as number of days from date zero. Age will be provided in years, at the time of the first troponin test.

Date of death will be converted to the number of days since date zero. All patients will be retrospectively followed up, using routinely collected data on the NHS Spine Application, Summary Care Record, until death or censoring on 1st April 2017.

Data elements

The database model will include 156 data points, grouped into demographics, emergency department attendance and inpatient episodes, biochemistry, diagnosis, angiography, revascularization, echocardiography and mortality. Diagnostic data will be based on International Statistical Classification of Diseases and Related Health Problems (ICD) discharge codes.

Outcomes

Primary outcome

The primary outcome will be all-cause mortality. The nature if the data sources means that this is the outcome that will be available and it will be available with high fidelity.

Secondary outcomes

The secondary outcomes will be:

- Acute coronary syndrome (ACS) diagnosis (unstable angina, non-ST segment elevation myocardial infarction (NSTEMI), ST-segment elevation myocardial infarction (STEMI))
- Non-ACS diagnosis
- Angiography
- Revascularisation (coronary artery bypass grafting CABG), percutaneous coronary intervention (PCI))

Statistical Methods

Baseline data

Baseline and demographic characteristics will be summarised by standard descriptive summaries:

- means (standard deviation) for continuous variables which are normally distributed
- median (interquartile range) for continuous variables which are not normally distributed
- number (percentage) for categorical variables

Age distribution

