Troponin has a marked positive skew. Therefore, we plan for the bands to be spaced not arithmetically but exponentially, with narrow spacing nearer low values, where there is a higher frequency density of troponin values.

Adopting this approach for analysis has the following advantages:

1. It allows the shape of the relationship to be explored without making assumptions about the shape in advance.
2. It allows values documented in the hospital databases as “less than X” or “more than X” to be used correctly in the analysis rather than omitted or have imputed values.
3. The resulting display of the mortality relationship should be easily interpreted and applied by clinicians.

All analyses on troponin will be performed using the peak troponin level. For patients who have a single troponin measurement, the peak troponin will be based on this measurement. In the remainder of the patients who have more than one

troponin test in the same hospital episode, the peak troponin value will be defined as the highest of all measurements.

Relationship between troponin positivity, age and mortality

To assess the association of dichotomous troponin level (above ULN or not) with all-cause mortality, Cox proportional hazards regression modelling will be used. Hazard ratios will be determined for the following age groups: 18-29, 30-39, 40-49, 50-59, 60-69, 70-79, 80-89 and 90+ years. We will also stratify the hazard ratios for troponin positive versus negative groups across these age groups by troponin assay (contemporary versus high-sensitivity troponin assay).

The Kaplan-Meier method will be used to calculate and display cumulative mortality, with positive and negative troponin bands compared using the log-rank statistic.

Relationship between troponin level and mortality

The main analysis of the association of progressively higher troponins with all-cause mortality will be performed without making assumptions about the shape of the relationship, i.e. with Cox proportional hazards regression modelling.

The Kaplan-Meier method will be used to calculate and display cumulative mortality, with troponin bands compared using the log-rank statistic. The results will be stratified according to ACS diagnosis and revascularisation status.

ACS diagnosis

The ICD-10 codes in Table 2 will be used to indicate an ACS diagnosis.

ICD-10 Code	Category
I20.0	Unstable angina
I21.0	Acute transmural myocardial infarction of anterior wall

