I21.1	Acute transmural myocardial infarction of inferior wall
I21.2	Acute transmural myocardial infarction of other sites
I21.3	Acute transmural myocardial infarction of unspecified site
I21.4	Acute subendocardial myocardial infarction
I21.9	Acute myocardial infarction, unspecified
I22.0	Subsequent myocardial infarction of anterior wall
I22.1	Subsequent myocardial infarction of inferior wall
I22.8	Subsequent myocardial infarction of other sites
I22.9	Subsequent myocardial infarction of unspecified site
I24.8	Other forms of acute ischaemic heart disease
I24.9	Acute ischaemic heart disease, unspecified

Table 2. ICD-10 codes used to indicate an ACS diagnosis

Revascularisation status

Acute revascularisation will be defined as having PCI or CABG in the time window between 48 hours before and 3 months after the first troponin measurement. This will account for patients who had revascularisation, in particular PCI, as an

emergency prior to their first troponin blood test and to capture revascularisation, in particular CABG, performed as an outpatient following their index admission.

Statistical package

Statistical analyses will be performed using SPSS software version 24 (SPSS Inc., Chicago, Illinois, United States) and the results verified by replicate analysis using R 3.3.2 statistical package (the R Core Team, Vienna, Austria).

Statistical significance

All hypothesis tests will be 2-tailed. A p-value of <0.05 will be considered statistically significant. No correction will be implemented for multiple testing.

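### The age-band Cox models specify no adjustment for age within bands of ten or more years, so each hazard ratio may carry a residual age effect that age in years, already in the dataset, would remove

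*Combined protocol and SAP*

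**What the plan says.** The section on troponin positivity, age and mortality gives the model: "To assess the association of dichotomous troponin level (above ULN or not) with all-cause mortality, Cox proportional hazards regression modelling will be used". It then gives the subgroups: "Hazard ratios will be determined for the following age groups", namely 18-29, six ten-year bands from 30-39 to 80-89, and 90+. The same contrasts are to be repeated by contemporary versus high-sensitivity assay: "We will also stratify the hazard ratios for troponin positive versus negative groups across these age groups by troponin assay". That makes eight hazard ratios overall and up to sixteen by assay type. No covariate is named for any of them.

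The section on the TROP-RISK study dataset states: "Age will be provided in years, at the time of the first troponin test". Under De-identification, "date of birth is transformed to year of birth", so age is known to about a year.

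These models concern the primary endpoint: "The primary outcome will be all-cause mortality". Under Statistical significance, tests are two-sided at 0.05 with no multiplicity correction. The documents give no number of patients or deaths, no positivity rate, no age gradient and no expected hazard ratio.

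**The concern.** Ten years is a wide interval for a mortality endpoint. If both the chance of a positive troponin and the death rate rise with age inside a band, the positive group is older than the negative group, and part of the hazard ratio is age. Where both gradients have the same sign, the bias is upward in every band, so it does not cancel when the bands are read together.

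The bias also depends on band width. The 18-29 band spans 12 years, the next six span ten, and 90+ has no upper limit. How the hazard ratio varies with age is what this section sets out to show, so an age component that differs by band affects its main product, whatever the true hazard ratios are.

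**Working it through.** The plan has no figure of its own to reproduce. The check asks how large a hazard ratio would appear if troponin had no effect at all.

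**Inputs from the documents:** the band limits, the absence of covariates, and two-sided alpha of 0.05.

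**Inputs assumed:** log-odds of positivity linear in age, with an odds ratio (OR) of 1.2 to 2.5 per decade; hazard log-linear in age, with slope g of 0.05 to 0.10 per year; 30% positive at the band midpoint; age uniform within closed bands; 90+ taken as 90-105 with numbers falling exponentially at 0.25 per year.

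**Step 1: formula.** False HR = (mean hazard in positives) / (mean hazard in negatives), integrated over the band. For a closed band of width W, with b = ln(OR)/10, a good shortcut is ln HR ≈ g × b × W²/12, because b × W²/12 approximates the age difference between positives and negatives.

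**Step 2: worked case.** Take OR 2.0 per decade (b = 0.0693) and g = 0.10.
- Ten-year band: 0.10 × 0.0693 × 100/12 = 0.058, so HR ≈ 1.059; integration gives 1.058.
- 18-29: 0.10 × 0.0693 × 144/12 = 0.083, so HR ≈ 1.087; integration gives 1.083.
- 90+: integration gives 1.096.

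With identical gradients, 18-29 therefore appears 1.083/1.058 = 1.024 times, and 90+ 1.096/1.058 = 1.036 times, the ratio in a ten-year band, purely from band width and shape.

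**Step 3: range over the assumed gradients (true HR = 1).**

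| Band | OR 1.2, g 0.05 | OR 2.0, g 0.10 | OR 2.5, g 0.10 |
|---|---|---|---|
| Ten-year | 1.008 | 1.058 | 1.077 |
| 18-29 | 1.011 | 1.083 | 1.110 |
| 90+ | 1.011 | 1.096 | 1.130 |

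These are not bounds. With OR 2.5 and g = 0.12 the figures would be 1.092, 1.132 and 1.163. The 90+ figure also depends on how fast numbers are assumed to fall with age.

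**Step 4: does adjustment remove it?** Cox models were simulated (20 runs of 10,000 patients per scenario) with and without age as a covariate. The ratio of unadjusted to adjusted HR was:
- ten-year band, OR 1.3, g 0.08: 1.020 (integration 1.017)
- ten-year band, OR 2.0, g 0.10: 1.057 (integration 1.058)
- 18-29, OR 2.5, g 0.10: 1.113 (integration 1.110)
- 18-29, OR 1.5, g 0.05: 1.023 (integration 1.024)

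The age term therefore removes about the amount that the integration predicts. Age in completed years did as well as exact age (HRs differed by less than 0.1%).

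**Step 5: when would the bias be called significant?** With D deaths in a band and a proportion p positive, the standard error of ln HR is 1/√(D p(1−p)). Deaths for an 80% chance of p < 0.05 are (1.960 + 0.842)² / (p(1−p)(ln HR)²):

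| False HR | p = 0.5 | p = 0.3 |
|---|---|---|
| 1.02 | 80,062 | 95,311 |
| 1.05 | 13,189 | 15,701 |
| 1.08 | 5,301 | 6,311 |
| 1.11 | 2,883 | 3,432 |

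Chance of a false rejection at p = 0.3:

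| Deaths in band | HR 1.02 | HR 1.05 | HR 1.11 |
|---|---|---|---|
| 100 | 5.1% | 5.6% | 7.7% |
| 1,000 | 5.9% | 10.9% | 32.7% |
| 5,000 | 9.8% | 35.3% | 92.2% |
| 20,000 | 25.0% | 88.5% | about 100% |

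**The case against.** **A reader might infer that the plan carries a known false excess.** It does not. The documents contain no data on age by troponin status or on mortality by age, so both the direction and the size rest on assumptions. The direction is plausible; the percentages are conditional. An excess of 11% does not arise in the ten-year bands under the gradients used here.

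**A reader might infer that so large a cohort is bound to declare the excess significant.** The documents do not support this. They give no patient or death counts, and a 2% excess would need some 80,000 to 95,000 deaths in one band. The largest bias among the closed bands is in 18-29, which probably has few deaths; with 100, a false HR of 1.11 is called significant 7.7% of the time. The argument also applies only where the true hazard ratio is close to 1. Elsewhere the result is a modest inflation of the estimate.

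**A reader might infer that adjustment is ruled out.** The plan is silent on it. Even so, an analyst who follows the text as written would fit troponin alone within each band.

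**These models already control age more than the rest of the plan does.** That is true: the main analysis of troponin level names no age control at all, and sex, comorbidity and site are named nowhere as covariates. This point is one part of a wider gap, but that does not make the age-band models right.

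**The plan speaks of association, so crude ratios are defensible as description.** This stands if they are labelled as such, and it is a reason to report both versions.

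**Conclusion.** The point holds in a conditional form. The age-band Cox models specify no age term within bands of 10 to 12 years or the open 90+ band, although age in years is in the dataset. If positivity and mortality both rise with age within a band, each hazard ratio is biased upward. The excess is about 1-8% in the ten-year bands and up to about 11% in 18-29 and 13% in 90+, for a positivity OR of 1.2-2.5 per decade and a hazard slope of 0.05-0.10 per year. Unequal band widths may also distort the comparison across age groups, and this does not require a true hazard ratio near 1. False significance does require that, together with thousands of deaths in the band. The change is worth making because the remedy is simple and the data are already held. It does not imply that a sizeable association would be overturned.

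**What to change.** Prespecify age in years at first troponin test as a continuous covariate in every age-group Cox model, overall and by assay type. Either a linear term within each band or one spline across all bands will do. Report the unadjusted band-specific ratios alongside, labelled as descriptive.

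The cost is one variable already in the dataset and a small modelling assumption: a functional form for age within the band, with proportional hazards for that term. The hazard ratio also becomes conditional on age. Holding only the year of birth is not an obstacle: completed years performed as well as exact age in the simulations. An age taken as year of test minus year of birth was not simulated, but it errs by less than a year, which is small against a ten-year band.

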ICHNT validate the data to ensure that the structure, data items, units and data types are in accordance with the standardised data model. Data will be rejected if validation fails. On rejection, the files will be archived and the data manager will contact the data provider to review the submission and resend once corrected. Once imported into the secure research database, data are subject to clinical validation by Cardiovascular clinical experts; these validations will be completed by the clinical researchers using de-identified data. Data will be reviewed for data completeness, spread and actual data point values. If data appears invalid it will be rejected.

Data quality reports will be generated and provided to the research team and local data provider after each submission. These will be reviewed after each submission to ensure all areas are populated.

Research Database software

The database is built using Microsoft SQL server 2014, Microsoft's principle database management system software. The installation of the software was carried out by certified technical consultants and tested by the trust ICT team and data warehouse team in accordance with Trust ICT procedures and policies.

Database management

The database is fully backed up on a daily basis. The back-ups are standardised for all Trust databases within the Trust data warehouse. Backups can be restored at any

point by warehouse staff. Data are secondary copies from clinical systems; at any point the participating Trusts can re-extract the data from primary sources. Each site will submit data on a quarterly basis to the database. Data integrity checks will be completed to ensure correct structure is maintained and duplicates are not present.

Once entered on the system, data will not be changed. All access will be 'read only' except via exception, approved by the research Informatics Programme Manager and Clinical Leads group.

The database will be managed by the data manager ([name]) and developer ([name]). Database changes are controlled by the research informatics Programme manager ([name]), and are sanctioned by the NIHR HIC Cardiovascular scientific steering committee (Chaired by [name]). All staff are substantive NHS employees at ICHNT.

Data extracts taken for research will be stored within the data warehouse and retained for the period specified in the data request. All information pertinent to the request will be retained and tracked by the data manager.

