The age distribution of patients who have a troponin measured will be compared with that of the general population using the World Health Organisation (WHO) population estimates for the UK.

Troponin data

Assay performance

Each Trust measures either troponin I or T using either contemporary or high-sensitivity assays. These tests yield results in different measurable ranges with unique cut-off points for the 99th percentile of the upper limit of normal (ULN). A summary table of the performance of each assay will be assembled.

Handling of troponin data

The study dataset will comprise all patients who have had a troponin measured at each of the five academic centres between 2010 (2008 for University College Hospital) and 1st April 2017.

In clinical practice, troponin levels are frequently dichotomised into “positive” (meaning above ULN) or “negative”. Troponin levels may have a progressive relationship with prognosis, too, but the shape of this relationship is not known across the full spectrum of values and making the assumption of a linear relationship of mortality with troponin (or log troponin) may not be secure.

For these reasons, we will treat the data in two ways.

1. We will dichotomise the peak troponin level as being either positive or negative based on the ULN for each troponin assay. This makes no assumption of the shape of the relationship.
2. To standardise the many troponin assays, we will scale the results using the ratio of the observed troponin value divided by the ULN for that particular troponin assay. For example, a patient with a troponin value of 96 using an assay which has an ULN of 40 would have a scaled result of $96/40 = 2.4 \text{ xULN}$.

In some hospitals and some assays, troponin values above a certain level are systematically reported as “more than X”. According to what the hospitals have reported so far, the threshold at which the system gives results like this is in all cases very high. In no case does this truncation of results occur below 10,000 xULN. We therefore plan to set the uppermost band to be “>10,000 x ULN”. This ensures that the unavailability of an explicit value does not affect the troponin band into which any result is allocated.

Similarly, no hospital has reported truncating lower values of troponin at a threshold that is higher than $\frac{1}{2} \text{ xULN}$. Therefore, we plan for the lowermost band to be “< $\frac{1}{2} \text{ xULN}$ ”.

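### The age-band hazard ratios for troponin positivity pool Trusts with no Trust stratum, so they are confounded by Trust if positivity and mortality are associated across the pooled Trusts

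*Combined protocol and SAP*

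**What the plan says.** All references are to the combined protocol and SAP.

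- **Relationship between troponin positivity, age and mortality.** Cox regression gives a positive-versus-negative hazard ratio for all-cause mortality in each of eight age bands. The plan then says "We will also stratify the hazard ratios for troponin positive versus negative groups across these age groups by troponin assay", with two classes: contemporary and high-sensitivity. That makes 8 overall and 8 x 2 = 16 assay-split hazard ratios. Kaplan-Meier curves follow, "with positive and negative troponin bands compared using the log-rank statistic". Neither the curves nor the test is planned by Trust or by assay class.
- **Assay performance.** "Each Trust measures either troponin I or T using either contemporary or high-sensitivity assays", and each assay has its own upper limit of normal.
- **TROP-RISK STUDY dataset.** Five centres contribute patients tested "between 2010 (2008 for University College Hospital) and 2017", followed "until death or censoring on 1st April 2017". De-identification goes further for the analysis file ("This includes further de-identification to remove dates"), and time is kept on a day scale: "All further dates are provided as number of days from date zero".
- **Database management.** "Each site will submit data on a quarterly basis to the database", so the source Trust of each record should be known centrally.

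No section names Trust as a covariate, stratum, cluster or random effect in any model. The word *stratify* in the sentence quoted first means separate hazard ratios for each assay class; it does not mean a Trust-specific baseline hazard.

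**The concern.** The cohort is everyone with a routine-care troponin test at five hospitals, so nothing in the design balances Trusts. Dichotomising at the assay's own upper limit of normal standardises the cut-off. It does not equalise who gets tested, what fraction is positive, or how high mortality is given age band and troponin status.

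When Trusts share one risk set, the positive group is weighted towards Trusts with high positivity and the negative group towards Trusts with low positivity. If mortality follows the same gradient, part of the difference between Trusts is counted as a troponin effect. If it runs the other way, part of the troponin effect is cancelled. The reported hazard ratio can then lie above or below the value that holds in every contributing Trust, and no planned output would show it.

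Pooling of all five Trusts is certain for the overall hazard ratios. For the split ones, if each Trust used one class throughout, five Trusts in two classes put at least three in one class. The other class could be a single Trust, where this problem does not arise.

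**Working it through.** The plan gives no expected hazard ratio, event count, or positivity or mortality by Trust, so it has no figure to reproduce. The check asks how far pooling could move a known hazard ratio.

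**From the documents:** five centres; two assay classes; entry from 2010 (2008 at one centre); common censoring on 1 April 2017. Taking 1 January as the start, follow-up runs 0-7.25 years, or 0-9.25 at the 2008 centre.

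**Assumed:** three equal Trusts pooled in one age band; true hazard ratio θ = 2.0 in every Trust; constant hazards; uniform entry.
- Large differences: positivity 30/40/50%, negative-group hazard 0.05/0.075/0.10 per year.
- Mild differences: positivity 35/40/45%, hazard 0.05/0.06/0.07 per year.

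**Formula.** For Trust k with positive fraction p and negative-group hazard λ, the numbers at risk at time t are proportional to S1 = p·exp(-θλt)·G(t) and S0 = (1-p)·exp(-λt)·G(t), with G(t) = 1 - t/7.25. Deaths are d1 = θλ·S1 and d0 = λ·S0. The large-sample Cox estimate β solves

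∫ [d1 - e^β·S1/(S0 + e^β·S1)·(d1 + d0)] dt = 0.

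For the plan as written, S and d are summed over Trusts first. For the stratified model the bracket is formed within each Trust and then summed. Each Trust's term is then zero at e^β = 2.0, so stratification recovers 2.00.

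**Hand check at the start of follow-up, large case, same direction**
- Positive: 2 x (0.3x0.05 + 0.4x0.075 + 0.5x0.10)/1.2 = 2 x 0.095/1.2 = 0.1583
- Negative: (0.7x0.05 + 0.6x0.075 + 0.5x0.10)/1.8 = 0.130/1.8 = 0.0722
- Ratio 2.19

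**Positivity order reversed**
- Positive: 2 x 0.085/1.2 = 0.1417
- Negative: 0.140/1.8 = 0.0778
- Ratio 1.82

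**Full solution over 0-7.25 years**

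| Case | Same direction | Reversed | Other four orderings | Stratified |
|---|---|---|---|---|
| Large | 2.17 | 1.80 | 2.08, 2.06, 1.89, 1.88 | 2.00 |
| Mild | 2.04 | 1.95 | 2.02, 2.02, 1.97, 1.97 | 2.00 |

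- Multiplying all hazards by 0.1 to 4, to span young to old bands, gives 2.13-2.19 or 1.77-1.82 (large) and 2.03-2.05 or 1.94-1.95 (mild).
- With a true hazard ratio of 1.0, the large case gives 1.10 or 0.91.
- More Trusts over a given range dilute the effect. With positivity graded over 20-40% and mortality over 1-1.5 times, three Trusts give 2.12 and five give 2.09.

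**When there is no confounding**
- Only positivity differs: 2.00.
- Only mortality differs (40% positive throughout, large-case hazards): 1.98 at the base hazards, 1.96 at twice, 1.94 at four times, so 1-3% low. This is non-collapsibility of the hazard ratio, not confounding.
- Both differ but are not associated (35/50/35% with 0.05/0.075/0.10): the start-of-follow-up ratio is 2 x (0.09/1.2)/(0.135/1.8) = 2.00, and the full solution is 1.98, as when only mortality differs.

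**Follow-up length.** With a constant hazard ratio, 0-7.25 and 0-9.25 years both give 2.00. If the hazard ratio is assumed to fall from 4.0 (to day 30) to 2.0 (to 1 year) to 1.3, with 40% positive and the 2008 centre forming a class alone, the two classes would read 1.55 versus 1.51 (flat hazard 0.05 per year), or 1.87 versus 1.79 (hazard 0.30/0.08/0.05 over the same periods), with no assay effect. A 1-year cut without Trust stratification leaves the large-case Trust bias at 2.19 or 1.82.

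**The case against.** The strongest reply is that the plan sets out to describe an association. An unadjusted hazard ratio in the pooled population is a legitimate descriptive quantity, and whether Trust distorts it depends on figures that the documents do not contain. That stands, and it is why this is a suggestion. It does not remove the reason to act: readers will take an age-band hazard ratio as what positivity means at a given age, and the stratified version is closer to that at almost no cost.

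Four stronger readings are tempting, and the documents do not support them.

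- *That the hazard ratios are biased.* Pooling is certain for the overall ones; bias is conditional. It is also not enough that positivity and mortality both differ between Trusts. They must be associated across Trusts, as the 35/50/35% case shows. The extremes (1.80 and 2.17) need perfect alignment or reversal; the other orderings lie between 1.88 and 2.08.
- *That the plan makes an invalid test of one assay class against the other.* No between-class test is planned. The issue is bias within each hazard ratio and how a descriptive split is read.
- *That unequal follow-up seriously distorts the assay comparison.* The only documented difference is the 2008 versus 2010 start. Its effect is nil under proportional hazards and small otherwise. A larger gap would need Trusts to have switched assay class part-way, which the documents do not report.
- *That Trust adjustment is ruled out.* The plan is silent; it does not exclude it.

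**Conclusion.** The point holds as a low-severity improvement, with medium confidence. For assumed large differences between three equal Trusts, pooling moves a true hazard ratio of 2.0 to between 1.80 (10% low) and 2.17 (8.5% high). For mild differences the range is 1.95 to 2.04 (2.5% low to 2% high). The effect is nil for a class made up of one Trust and nil if only positivity differs. If only mortality differs, the pooled value is 1-3% low at one to four times the base hazards, through non-collapsibility. Trust positivity, mortality and size, and the true hazard ratio, are all assumptions, so these figures show what is possible and not what will occur.

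**What to change.** In the section on troponin positivity, age and mortality:

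1. Stratify the Cox baseline hazard by Trust for both the 8 overall and the 16 assay-split hazard ratios. Keep the unstratified hazard ratio as a sensitivity analysis, so that any gap between the two is visible.
2. Confirm that the de-identified analysis extract keeps a (coded) Trust identifier.
3. Tabulate assay by Trust. Where no Trust used both classes, label the assay contrast as between Trusts and descriptive. Trust stratification removes confounding within a class but cannot separate assay from Trust.

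**Cost.** This is SAP wording, with no new data if the Trust code is in the extract. Under the assumptions above, stratification keeps 95-98% of the information on the hazard ratio with large differences and about 99% with mild ones. Those are large-sample figures. In age bands with few deaths, a Trust with only positives or only negatives left at risk adds nothing at that point, so the loss could be greater there.

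**Optional.** A proportional-hazards check, and a hazard ratio to a common 1-year horizon beside the all-follow-up one. The day-scale times allow this without calendar dates. It does not replace Trust stratification and it is less precise: for the documented windows the calculated standard errors are 1.4 to 1.9 times those for all follow-up.
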